9.3 SUBJECT DEATH

9.3.1 Procedure for recording and reporting subject death

- All subject deaths are to be documented and reported to the sponsor as soon as possible but no later than 10 days after becoming aware of the event. Notification of death should include a detailed statement of the pertinent events and be signed by the investigator in addition to the appropriate case report forms (Death, Withdrawal, and Product Out of Service CRFs). It is the investigator's responsibility to notify the IRB/EC per the IRB/EC policy. Details of death and the following information, if available, should be provided in a letter to St. Jude Medical by the investigator summarizing the patient's course since enrollment in the study:
 - Date and time of death
 - Place death occurred (e.g. hospital, nursing home, patients home)
 - If death was witnessed
 - Identification of the rhythm at the time of death, if known (include any available documentation)
 - Cause of death
 - Any other circumstances surrounding the death
 - Approximate time interval to death from the initiating event.
 - Autopsy report (if performed)
 - Whether it was device and/or procedure related
 - Whether it was related to the study
 - Device configuration at the time of death

Provide clinical notes and witness statements. If possible, interrogate the pulse generator. Retrieve and print all episode diagnostics, IEGMs, and programmed parameters. If applicable, the pulse generator should then be programmed OFF.

Every attempt should be made to explant the pulse generator and/or leads intact. Any explanted devices or leads should be returned to St. Jude Medical for analysis promptly. In the event that the device is not explanted, the above procedure must be followed to retrieve the data. The reason the pulse generator and/or lead(s) are not being returned to St. Jude Medical must be stated clearly on the case report form.

9.4 DEVICE COMPLAINTS

A device complaint is defined as any written, electronic, or oral communication that alleges deficiencies related to the identity, quality, durability, reliability, safety, effectiveness or performance of a device after it is released for distribution.

Device complaints include malfunctions, use errors and inadequate labeling.

Device complaints in St. Jude Medical market-released products must be reported per St. Jude Medical product surveillance process. Please notify SJM Tech Service via email at [REDACTED].

Clinical Investigational Plan

10.0 DATA MANAGEMENT

Overall, the Sponsor will be responsible for the data handling.

The sponsor and/or its affiliates will be responsible for compiling and submitting all required reports to governmental agencies.

Data will be analyzed by the Sponsor and may be transferred to the Sponsor's locations outside of US and/or any other worldwide regulatory authority in support of a market-approval application.

St. Jude Medical respects and protects personally identifiable information that we collect or maintain. As part of our commitment, St. Jude Medical is certified to the U.S. - European Union Framework and U.S. – Swiss Safe Harbor Framework Agreements regarding human resources and subject clinical trial personal information. The privacy of each subject and confidentiality of his/her information will be preserved in reports and when publishing any data. Confidentiality of data will be observed by all parties involved at all times throughout the clinical study. All data will be secured against unauthorized access.

Data and additional source documents will be submitted through EDC.

The Principal Investigator or institution will provide direct access to source data during and after the clinical study for monitoring, audits, IRB/EC review and regulatory authority inspections. As required, the Principal Investigator or institution will obtain permission for direct access to source documents from the subject, hospital administration and national regulatory authorities before starting the clinical study.

10.1 DATA MANAGEMENT PLAN

A detailed Data Management Plan will be established to ensure consistency of the data. This document will include procedures used for data review, database cleaning, and issuing and resolving data queries. If appropriate, the DMP may be updated throughout the study duration. All revisions will be tracked and document controlled.

CRF data will be captured in a validated electronic database management system hosted by St. Jude Medical.

Only authorized site personnel will be permitted to enter the CRF data through the electronic data capture (EDC) system deployed by St. Jude Medical. An electronic audit trail will be used to track any subsequent changes of the entered data.

10.2 DOCUMENT AND DATA CONTROL

10.2.1 Traceability of documents and data

The investigator will ensure accuracy, completeness, legibility and timeliness of the data reported to the sponsor on the CRFs and in all required reports.

Clinical Investigational Plan

10.2.2 Recording data

Source documents will be created and maintained by the investigational site team throughout the clinical study.

The data reported on the CRFs will be derived from, and be consistent with, these source documents, and any discrepancies will be explained in writing.

The CRFs will be signed and validated by the authorized site personnel.

11.0 MONITORING

Centralized monitoring will occur through routine internal data review. This monitoring is designed to identify missing and inconsistent data, data outliers, and potential protocol deviations that may be indicative of site non-compliance. On site monitoring may occur at the discretion of the sponsor.

12.0 STATISTICAL CONSIDERATIONS

The following section describes the statistical methods for the clinical investigation design.

12.1 STATISTICAL DESIGN, HYPOTHESES, METHOD AND ANALYTICAL PROCEDURES

This is a prospective, multicenter, non-randomized registry/observational study. Analysis of the study objectives will be summarized using data collected upon 12-month follow-up visit by the groups defined in section 3.2. The objectives of this study will be summarized as the follows:

- Overall CRT response rate at 12 months will be summarized by percentages with a 95% confidence interval using exact method for binomial distribution.
- QOL, LVEF, and LVESV at baseline, 3, 6, and 12 months will be summarized by means (\pm standard deviation), median and range.
- Programming timing and workflow between implant and 12 months will be summarized by frequency and percentage for categorical data.
- Rates of heart failure (HF) hospitalization events at 12 months, cardiovascular hospitalizations at 12 months, and HF 30-day hospitalization rates will be summarized using Kaplan-Meier method.
- Costs associated with HF-related health care utilizations at 12 months will be summarized by means (\pm standard deviation), median and range.
- All-cause mortality at 12 months will be summarized using Kaplan-Meier method.

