3.2.1 Number of subjects required to be included in the study

The study will enroll up to 2,000 patients with successful SJM CRT MP device implant from up to 140 centers undergoing CRT implantation. Any patient who received a market approved SJM Quadra Allure MP, Quadra Assura MP, or newer SJM CRT MP device is eligible for enrollment in the study.

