5.2 Evaluation of responder status

Patients' responder status will be assessed at 3, 6 and 12 months post implant using the CCS. The CCS includes four components: NYHA class, Patient Global Assessment (PGA), HF events, and cardiovascular death.²¹

The **NYHA Class assessment and PGA** are determined by a designated assessor interviewing patients about their symptoms. Specifically, the PGA will be a single interview question asking the patient to categorize how they feel compared to their previous visits as either:

- Markedly better
- Better
- No change
- Worse
- Markedly worse

At the 3, 6 and 12-month visits, a PGA will be conducted to evaluate how the patient feels compared before having the CRT system implanted.

In this trial, a **HF event** is defined as any one of the following when the subject has symptoms and/or signs consistent with congestive heart failure:

- Hospitalization for HF \geq 24 hours
- Clinic or hospital visit for HF < 24 hours (i.e. outpatient treatment, observational care, ER, Urgent Care and physician's office visit) requiring administration of IV diuretics, inotropes, and/or vasodilators

Finally, **cardiovascular death** is defined as sudden unexpected death; heart failure death; myocardial infarction related death; or 'other' death, such as deaths due to pulmonary embolism, peripheral thromboembolism, stroke, vascular procedure, or other major cardiovascular event.

Using the CCS and decision algorithm described in section 5.2.1 patients are categorized as Improved, Worsened or Unchanged based on the following rules:

- “Improved” – patients demonstrating:
 - At least a one-class improvement in NYHA Class OR improvement by PGA (“better” or “markedly better”)
AND
 - No HF events as described above
AND
 - No cardiovascular death
- “Worsened” – patients demonstrating:
 - Worsening in NYHA Class OR worsening by PGA (“worse” or “markedly worse”)

OR

[figure not shown]

Clinical Investigational Plan

- Presence of HF events as described above
OR
 - Cardiovascular death
- “Unchanged” – patients neither “Improved” nor “Worsened”.

Patients who are “Improved” or “Unchanged” using the above definition will be grouped together as Responders. Patients classified as “Worsened” will be considered Non-Responders.

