12.3 MAXIMUM NUMBER OF SUBJECTS TO BE INCLUDED FOR EACH CENTER

The maximum number of subjects that each center can enroll is 300.

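### The exact binomial interval for the 12-month response rate ignores centre; it will be too narrow if response is correlated within centres and the result is meant to apply beyond them.

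*Combined protocol and SAP*

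**What the plan says.** Section 12.1 sets the method for the first-listed outcome, the overall response rate at 12 months, which is to be summarised by "percentages with a 95% confidence interval using exact method for binomial distribution". It is the only confidence interval specified in that section. The same section says the objectives "will be summarized using data collected upon 12-month follow-up visit by the groups defined in section 3.2", that is, by the four pacing groups of section 3.2.

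On size and spread, section 3.2.1 states: "The study will enroll up to 2,000 patients with successful SJM CRT MP device implant from up to 140 centers undergoing CRT implantation". Section 12.3 adds: "The maximum number of subjects that each center can enroll is 300".

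The visible text has no centre term, clustered variance, design effect, ICC or check that centres can be pooled. Section 12.2 (sample size) is redacted, so it cannot be known whether clustering was considered there. The method in section 12.1 is not redacted.

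**The concern.** The exact binomial interval has its stated coverage when patients respond independently with a common probability. Two features of the plan make some correlation within centres plausible:

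- Under section 5.2, NYHA class and the Patient Global Assessment (PGA) "are determined by a designated assessor interviewing patients about their symptoms". NYHA class comes out of that interview, so patients of one centre may share an assessor's habits. The PGA category is the patient's own answer and gives less ground for this.
- Under section 5.5, the choice between BiV and MPP programming is left to the physician at every visit. Programming also defines the groups whose rates are reported.

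Section 3.1 gives the purpose as describing how the technology is used in real-world practice. If that means practice beyond the enrolled sites, the interval should carry the variation between centres, and the binomial interval leaves it out. In a descriptive study the estimate and its interval are the result, so the stated confidence should be right.

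**Working it through.** The visible text gives no expected response rate, interval width or ICC, so there is no figure of the plan's own to reproduce.

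**Inputs from the plan.** Up to 2,000 patients and up to 140 centres (section 3.2.1), so 2,000/140 = 14.3 per centre at both maxima; at most 300 per centre (section 12.3), so 300/2,000 = 15% of the total; 95% exact interval (section 12.1), taken as two-sided.

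**Assumptions.** ICC from 0 to 0.05; response rate 70%; all 2,000 assessed at 12 months.

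**Step 1. Weighted cluster size**, m_w = Σm² / Σm.
- 140 equal centres: 14.29.
- One centre of 300 and 139 sharing 1,700: (300² + 1,700²/139)/2,000 = (90,000 + 20,791)/2,000 = 55.40.

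**Step 2. Design effect**, DE = 1 + (m_w − 1) × ICC. For example, equal centres at ICC 0.05: 1 + 13.29 × 0.05 = 1.66. One centre at 300: 1 + 54.40 × 0.05 = 3.72.

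**Step 3. Consequences.** Effective n = 2,000/DE, with the exact interval recomputed at that n. Approximate coverage of the unadjusted interval = 2Φ(1.96/√DE) − 1. Coverage was also simulated with beta-binomial centres, 20,000 runs per scenario.

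| Centres | ICC | DE | Half-width at effective n (points) | Coverage, formula | Coverage, simulated |
|---|---|---|---|---|---|
| Equal | 0 | 1.00 | 2.03 | 95.0% | 95.0% |
| Equal | 0.01 | 1.13 | 2.16 | 93.4% | 93.7% |
| Equal | 0.02 | 1.27 | 2.29 | 91.9% | 92.2% |
| Equal | 0.05 | 1.66 | 2.63 | 87.1% | 87.7% |
| One of 300 | 0 | 1.00 | 2.03 | 95.0% | 95.4% |
| One of 300 | 0.01 | 1.54 | 2.53 | 88.5% | 88.8% |
| One of 300 | 0.02 | 2.09 | 2.95 | 82.5% | 82.9% |
| One of 300 | 0.05 | 3.72 | 3.96 | 69.0% | 69.6% |

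The unadjusted half-width is 2.03 points throughout. A separate simulation at 80% response, ICC 0.01 to 0.05, gave the same picture: 94% to 88% with equal centres and 89% to 70% with one centre at 300.

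**Step 4. By pacing group.** Group sizes are not given. Assume a group of 500; the coverages below are from the formula, for ICC 0.01 and 0.05.
- Spread evenly over equal centres: m_w = 14.29/4 = 3.57, DE 1.03 and 1.13, coverage 94.7% and 93.5%.
- Spread evenly, one centre of 300 in the study: m_w = 55.40/4 = 13.85, DE 1.13 and 1.64, coverage 93.5% and 87.4%.
- Concentrated, with 150 of the 500 in one centre and 350 over 139 others: m_w = (150² + 350²/139)/500 = 46.8, DE 1.46 and 3.29, coverage about 90% and 72%.

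**Step 5. Does a clustered interval do better?** Korn-Graubard intervals simulated at 80% response and N = 2,000 covered about 94% to 96% with equal centres or one at the cap. With ICC near 0 the half-width rose only from 1.78 to about 1.83 points. With two centres at the cap coverage was about 93% to 91%, and with six about 89% to 88%.

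**The case against.** A reader might infer that the interval is certainly too narrow. The documents do not support that, for these reasons.

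- **No ICC is given.** At ICC 0 coverage is 95%. With equal centres and ICC 0.01 the half-width grows by only 2.16 − 2.03 = 0.13 points. This stands, and the point is therefore conditional. It does not weaken the remedy, which estimates the correlation from the trial's own data.
- **The target of inference is not stated.** For the response rate of the participating centres alone the exact interval is not too narrow: simulated coverage was 95.2% to 95.9%, even with several centres at the cap. This stands too. The purpose in section 3.1 points to a wider target but does not settle it.
- **The 300 is a ceiling, not a planned size.** Nothing says that any centre will approach it, so the 70% figure is a what-if. Equally, nothing limits it to one centre.
- **Reporting is by pacing group**, where clusters are smaller and the effect weaker unless a group concentrates in a few centres. Also, 2,000 is an upper limit on enrolment, not the number assessed at 12 months.
- **Little depends on it.** Section 12.1 says: "This is a prospective, multicenter, non-randomized registry/observational study". No test, threshold or decision rule is visible, and an unadjusted interval for a descriptive proportion is a defensible choice.

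Two further inferences should be resisted. The documents do not say that admission practice differs between centres. The redaction of section 12.2 is not evidence that clustering was overlooked.

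**Conclusion.** The concern holds in conditional form. The planned interval ignores centre; if the ICC is above 0 and the result is meant to reach beyond the enrolled sites, its coverage is below 95% by an amount the documents do not fix. Over the assumed ICC range of 0 to 0.05 and with 2,000 patients, the loss runs from nothing to about 7 points of coverage with equal centres, and to about 25 points if one centre reaches the cap. For an evenly spread group of 500 from equal centres it is at most about 1.5 points.

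This affects the stated precision of a descriptive summary. It does not bias the estimate or overturn a decision. It is worth correcting because a better interval is available at almost no cost from data already collected.

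**What to change.** In section 12.1:

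- Report the 12-month response rate, overall and for each section 3.2 group, with a centre-clustered 95% interval: Korn-Graubard, that is, Clopper-Pearson on the effective sample size with centre as the cluster.
- Report the estimated ICC and the distribution of centre sizes beside it.
- Keep the unadjusted exact interval as a sensitivity result.
- State the limit of the method: if two or more centres approach 300, the clustered interval may itself cover only about 88% to 93%.

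The cost is a few sentences in the plan and a slightly wider interval when the ICC is small. No new data and no change in conduct are needed, provided centre is recorded for each patient.

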3.0 STUDY DESIGN

3.1 Purpose

The purpose of this post market study is to characterize real-world use of MPP technology in patients indicated for a CRT device.

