3.2 Study Design and Scope

This is a prospective, multicenter, non-randomized registry/observational study. All subjects who meet inclusion criteria, do not meet exclusion criteria, sign an IRB/EC approved informed consent, complete a Baseline visit prior to device implant and have an attempted implant of the SJM Quadra Allure MP, Quadra Assura MP, or newer SJM CRT MP device will be considered enrolled in the study. MPP programming guidelines are provided in Appendix I. Patients will be followed for 12 months after implant. Data will be collected at post-implant (within 30 days of successful CRT device implant), 3, 6, 12 months and during any unscheduled follow-up visit. At 12 months, the responder rate will be evaluated among the following groups:

- MPP Group: MPP ON within 1 month post implant and then continuously programmed ON until 12 months (i.e., MPP ON for months 1-12 continuously)
- Treatment Strategy (BiV/MPP) Group: MPP ON at the 12-month study visit and for at least 3 continuous months prior to 12-month assessment (i.e., BiV ON at some point in months 1-9 and MPP ON for months 10-12)
- BiV Group: MPP OFF at the 12-month study visit and for at least three continuous months prior to 12-month assessment (i.e., BiV ON for months 10-12)
- Other Pacing Group: Other pacing schemes not covered above (Retrospective categorization implemented based on the usage of MPP or BiV for 12 months)

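### Three of the four section 3.2 groups require pacing status up to month 12, so their mortality is near zero by construction and their response and hospitalization results are conditional on survival; they can describe practice but cannot show an impact of MPP

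*Combined protocol and SAP*

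**What the plan says.** Section 12.1 sets the frame: "Analysis of the study objectives will be summarized using data collected upon 12-month follow-up visit by the groups defined in section 3.2". Within it:

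- Response on the Clinical Composite Score (CCS) gets a percentage with an exact 95% interval.
- Heart failure (HF) and cardiovascular hospitalization get Kaplan-Meier estimates, and so does mortality: "All-cause mortality at 12 months will be summarized using Kaplan-Meier method".
- Costs get mean, SD, median and range. The continuous outcomes are treated the same way: "QOL, LVEF, and LVESV at baseline, 3, 6, and 12 months will be summarized by means", again with SD, median and range. Change from baseline is not listed.

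Section 3.2 defines the groups:

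- MPP Group: "MPP ON within 1 month post implant and then continuously programmed ON until 12 months".
- Treatment Strategy Group: "MPP ON at the 12-month study visit and for at least 3 continuous months prior to 12-month assessment".
- BiV Group: "MPP OFF at the 12-month study visit and for at least three continuous months prior to 12-month assessment".
- Other Pacing Group: whatever the first three do not cover, with the note "Retrospective categorization implemented based on the usage of MPP or BiV for 12 months".

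Section 5.5 leaves programming to the physician at every visit, and section 8.0 says MPP can be turned off in a patient who does not benefit. Section 5.2 makes a cardiovascular death a non-response.

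The purpose in section 3.1 is descriptive: "The purpose of this post market study is to characterize real-world use of MPP technology in patients indicated for a CRT device". Section 3.3 goes further and seeks the impact of MPP on response, quality of life, echo measures, hospitalization, cost and mortality. Section 6.1 wants to assess cost differences among the groups.

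**The concern.** Group membership depends on what happens after implant, up to the time at which the outcome is read. For mortality this is circular: a patient must reach month 12, or the 12-month visit, to be counted in a group whose 12-month mortality is then estimated. The same condition removes cardiovascular deaths from the CCS response rate. It also removes the hospitalizations and HF-related costs of patients who die or leave early.

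Readers will compare the group columns. Near-zero mortality under both MPP and BiV pacing could be taken as a property of the pacing. Differences in response or cost would mix any MPP effect with case mix and with the reasons why physicians changed the programming.

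A lesser matter is that visit-level means and SDs do not give the precision of a change from baseline. For echo, the patients behind each visit mean may differ.

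**Working it through.** The plan shows no figure to reproduce; section 12.2 is redacted. Step 1 follows from the text. In steps 2 to 5 every input is an assumption except the enrollment ceiling of 2,000 (section 3.2.1).

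**1. Can a patient who dies at month 8 enter a named group?** MPP Group: no, because MPP must stay on until month 12. Treatment Strategy and BiV Groups: no, because status at the 12-month visit is required. Other Pacing: not stated. The one gap is the visit window of ±45 days (section 5.5): a patient seen up to 45 days early could die before the anniversary. Section 9.2 ends safety reporting at the last visit, so such a death might not be reported. Hence near zero rather than exactly zero.

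**2. Mortality.** If 5-10% die within 12 months, deaths = 0.05 × 2,000 = 100 to 0.10 × 2,000 = 200. The whole-cohort figure is 5-10%; the three named groups show about 0%. If the deaths are placed in Other Pacing together with survivors equal to 5-20% of the cohort (100-400), crude mortality there runs from 100/(100 + 400) = 20.0% to 200/(200 + 100) = 66.7%. If they are left unclassified, they appear in no column.

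**3. Response.** Suppose 80% respond among patients without cardiovascular death, and 3-8% of the cohort die of cardiovascular causes. Whole-cohort response = 80 × (1 − 0.03) = 77.6% to 80 × (1 − 0.08) = 73.6%. The named groups still read 80%, which is 2.4 to 6.4 points higher.

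**4. MPP against BiV when pacing has no effect.**

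By hand: 1,000 patients start on each mode and all survive; 200 in each do poorly early and 800 do well. By month 9, 30% of the poor and 10% of the others change mode. Response is 50% and 85% respectively, whatever the pacing.

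- MPP Group: 140 poor, 720 good; (70 + 612)/860 = 79.3%.
- Treatment Strategy: 60 poor, 80 good; (30 + 68)/140 = 70.0%.
- BiV Group, including those switched off MPP: 200 poor, 800 good; (100 + 680)/1,000 = 78.0%.

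MPP minus BiV is +1.3 points and Treatment Strategy minus BiV is −8.0. If 20% rather than 10% of the others change mode, the differences are +0.7 and −2.5.

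By simulation (1,000,000 patients per scenario): half start on MPP. At average frailty, 15% worsen by month 6, which persists, and 10% worsen later. Mortality is about 6%, frailty raises both risks, and all deaths count as non-response.

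- No switching, start mode unrelated to frailty: MPP 74.0%, BiV 74.2%; all patients about 69%.
- 25% or 50% of worsened patients change mode: 77.3% vs 74.1% and 80.9% vs 74.0%, false gains of 3.2 and 6.9 points.
- Less frail patients more often started on MPP: 77.4% vs 70.8% without switching, and 83.5% vs 72.2% with 50% switching, false gains of 6.6 and 11.3 points.

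**5. Change from baseline.** With equal SDs, SD of change = SD × √(2(1 − r)). For an SD of 25 at both visits, this is 29.6 at r = 0.3 and 19.4 at r = 0.7. The visit SDs do not reveal r.

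For echo, let m be the share not imaged at follow-up and d the amount by which imaged patients start lower, with no true mean change and complete baseline echo. The visit mean shifts by −r·m·d and the paired change by (1 − r)·m·d. With r = 0.7, m·d from 0.4 × 2 = 0.8 to 0.6 × 4 = 2.4 gives −0.56 to −1.68 for the visit mean and +0.24 to +0.72 for the paired change. Pairing is less biased here, but not unbiased.

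**The case against.** The best defense is that this is a descriptive registry. Its purpose is to characterize use, no between-group test is visible, and the redaction of section 12.2 cannot be held against it. Visit-level summaries are usual in such a study. Patient-level values are collected, so paired change could be computed without being listed. The CCS already refers to baseline through NYHA change and the global assessment. All of that stands: the summaries are not wrong as description, and the missing change score alone would be a small matter.

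The response bullet in section 12.1 also carries the word overall, which might promise a pooled rate. But the section's lead sentence puts every objective by group, and the mortality and hospitalization bullets have no such word.

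Three stronger readings are tempting, and the documents do not support them:

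- A reader might infer that early deaths will pile up in Other Pacing. Section 3.2 does not say so. They could go there, be left unclassified or be excluded, so the 20-67% in step 2 is only one reading.
- A reader might infer that survival conditioning favors MPP over BiV. It applies to both. Without switching or confounding, the simulation gives practically equal rates, both too high against the whole cohort.
- A reader might infer that a baseline-adjusted MPP-versus-BiV contrast is the missing remedy. It would use the same post-implant groups, and baseline covariates cannot undo selection that happens after baseline.

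What the defense does not answer is that a mortality column near zero by definition fails even as description, and that sections 3.3 and 6.1 ask for more than description.

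**Conclusion.** The point holds in this form. Read literally, the section 3.2 definitions keep almost all deaths before month 12 out of the MPP, Treatment Strategy and BiV groups. Group-wise Kaplan-Meier mortality is then not an estimate of mortality under each pacing mode. Response, hospitalization and cost results in these groups describe patients who survived and stayed in follow-up. They can serve as description, but they cannot support an impact of MPP or cost differences attributable to pacing mode.

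Only the near-zero mortality in the three named groups follows from the definitions. Every other size is illustrative: 2.4-6.4 points in response against the whole cohort, and a false MPP-minus-BiV difference from about zero to 11 points depending on assumed switching and case mix. The change should be made before analysis. The registry remains valid for its stated purpose.

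**What to change.** In section 12.1:

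1. Report 12-month mortality, HF and cardiovascular hospitalization, and CCS response for the whole implanted cohort, with early deaths counted. Say how a non-cardiovascular death enters the response rate, since section 5.2 names only cardiovascular death. State in which group early deaths and withdrawals are placed. Do not present the group-wise Kaplan-Meier curves as mortality under each pacing mode.
2. Add paired change from baseline, with SD and 95% CI, for MLWHF, EQ-5D and, where both values exist, LVEF and LVESV. Give the number of pairs, and state that this does not cure selective availability.
3. Show baseline characteristics by group. Limit sections 3.3 and 6.1, and the matching objective in the synopsis, to description or association.

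An adjusted MPP-versus-BiV contrast is not part of this fix.

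The cost is about one paragraph and a few extra tables. No new data are needed: Table 1 already schedules NYHA class, MLWHF, EQ-5D and the cardiac medications list at baseline. Whether other baseline items are available cannot be judged, because the case report forms are held separately (Appendix F). The results remain observational.
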